8.8.6. Additional Exploratory Endpoint #2

1-year composite of all-cause mortality or all-stroke rates.

Hypothesis/Decision criteria:

Version 5.0

Page 18 of 21

No specific hypotheses or pass/fail criteria have been set. The analysis will be descriptive, and no statistical hypothesis test will be performed.

Endpoint Definition/Parameters to Be Estimated:

Composite of all-cause mortality or all-stroke event rate estimate will be provided at 12 months post-procedure.

Data Collection and Analysis Dataset:

Data will be collected on an CEC CRF. This objective will be analyzed for both the attempted implant set, per-protocol (PP) set 1 for TAVR care pathway cohort, and per-protocol (PP) set 2 for Conduction Disturbance pathway.

Analysis Method:

A Kaplan-Meier analysis will be performed.

8.9. Safety Evaluation

Primary and secondary safety endpoints will be summarized as noted in Section 8.7 of this SAP. Adverse events will be provided in a listing and summarized.

The below 3 listings will be provided for the attempted implant set:

- A listing of deaths and reasons for deaths.
- A listing of adverse events with AE start and end dates, severity, outcomes, and procedure/device relatedness.
- A listing of device deficiencies.

9. Analysis for FX Addendum

9.1. Introduction

The Optimize PRO Clinical Investigation Plan (Parent protocol or Parent CIP) is the governing document for Optimize PRO Clinical Investigation Plan - FX Addendum. The purpose of the FX Addendum is to provide details and requirements for analysis unique to participation in the FX Addendum portion of the study.

9.2. Objective

The purpose of this analysis to collect post-market clinical evidence in the United States, on valve performance and procedural outcomes associated with the Evolut FX Device.

Version 5.0

Page 19 of 21

Medtronic

9.3. Endpoints

9.3.1. **Primary Endpoints**

The primary endpoint is the rate of all-cause mortality or all stroke at 30 days.

Secondary Endpoints 9.3.2.

The following are the secondary endpoints:

- Median days from index procedure to discharge
- Percentage of subjects with ≥ moderate aortic regurgitation (AR) at discharge
- Rate of pacemaker implant for new onset or worsening conduction disturbance at 30 days
- Percentage of subjects with an NCC depth of implant between 1.0 and 5.0 mm
- Percentage of subjects with an absolute canting value |NCC-LCC| of ≤ 2.0 mm

9.3.3. Additional Exploratory Endpoints

The following are additional exploratory endpoints:

- 30-day and 1-year hospital re-admission rates
- 1-year composite of all-cause mortality or all-stroke
- Percent of patients with a major vascular complication
- Percent of patients that require a recapture or resheath of the TAV
- Percent of patients in which the target depth of implant was achieved
- Orientation of valve relative to native anatomy

9.4. Sample Size

The sample size for the attempted implant population is approximately 150 subjects at approximately 10 sites in the US.

9.5. Statistical Methods

Refer to Section 8 for details on the statistical analysis for the Optimize PRO study. The roll-in analysis set will not be applicable for the FX Addendum. The analysis will be descriptive, and no statistical hypothesis tests will be performed.

Version 5.0

Page 20 of 21

The attempted implant set, implanted set, PP set 1 for TAVR care pathway, and PP set 2 for conduction disturbance pathway will be defined the same for subjects enrolled in the FX Addendum.

The primary analysis cohort for the primary endpoint and secondary safety and effectiveness endpoints will be the attempted implant set. Secondary and additional exploratory endpoints will be analyzed for both the attempted implant set, per protocol (PP) set 1 for TAVR care pathway cohort, and per protocol (PP) set 2 for Conduction Disturbance pathway. However, Percentage of subjects with an NCC depth of implant between 1.0 and 5.0 mm, Percentage of subjects with an absolute canting value |NCC-LCC| of ≤ 2.0 mm, Percentage of subjects in which the target depth of implant was achieved, and Echocardiography data will be analyzed based on the implanted set.

All post-reintervention echocardiographic data will be excluded from hemodynamic analyses unless specified otherwise. Echocardiographic assessments after the first reintervention date will be excluded from any analyses using echo data. Reinterventions will be based on CEC adjudication.

Changes to Planned Analysis 10.

The planned analyses in this SAP are aligned with the planned analyses noted in the CIP (6.0, 04 May 2021). Additionally, all analyses defined for the FX Addendum are consistent with the version of the Addendum for which this plan was developed (3.0, 15 December 2022).

11. **Validation Requirements**

Level 1 validation (independent validation) will be used for the analysis datasets and the primary and secondary endpoints. Level 2 validation (peer review) will be used for additional analyses, data summaries, and listings.

References 12.

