5.2. Endpoints

The following endpoints will be used to evaluate valve performance and procedural outcomes associated with the Evolut™ FX System.

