8.3. Missing Data

Every effort will be undertaken to minimize missing data. However, some missing data is inevitable, and the trial is designed with the expectation that there may be up to 6% of primary data missing at 12 months. Unless otherwise specified, no statistical techniques will be used to impute missing data. The number of subjects included in each analysis will be reported so that the reader can assess the potential impact of missing data.

In the case of partial dates, if only the month and year are known, the event or assessment will be analyzed as if it occurred on the 15th of that month. If only the year is known, the event or assessment will be analyzed as if it occurred on June 30th of that year. These resolutions of partial dates are subject to the restrictions that events must occur no earlier than the procedure date.

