8.8.2. Secondary Endpoint #1

Median days from index procedure to discharge.

Hypothesis/Decision criteria:

No specific hypotheses or pass/fail criteria have been set. The analysis will be descriptive, and no statistical hypothesis test will be performed.

Endpoint Definition/Parameters to Be Estimated:

Days from index procedure to discharge will be summarized.

Data Collection and Analysis Dataset:

Data will be collected on a Procedure (PROC) and/or Discharge (DISC) CRF. This objective will be analyzed for the attempted implant set, per-protocol (PP) set 1 for TAVR care pathway cohort, and per-protocol (PP) set 2 for Conduction Disturbance pathway.

Version 5.0

Page 16 of 21

Analysis Method:

Descriptive statistics will be provided. The mean, median, standard deviation, minimum, maximum, and first and third quartiles will be presented.

Secondary Endpoint #2 8.8.3.

Percentage of subjects with \geq moderate agric regurgitation (AR) at discharge.

Hypothesis/Decision criteria:

No specific hypotheses or pass/fail criteria have been set. The analysis will be descriptive, and no statistical hypothesis test will be performed.

Endpoint Definition/Parameters to Be Estimated:

Aortic valve function will be based on core lab echocardiographic recordings. The parameter to be estimated is the grade of aortic valve regurgitation using echo, in subjects at discharge.

Data Collection and Analysis Dataset:

Data will be collected on Core lab ECHOCARDIOGRAM CRF. This objective will be analyzed for both the implanted (IMP) set, per-protocol (PP) set 1 for TAVR care pathway cohort, and perprotocol (PP) set 2 for Conduction Disturbance pathway. In addition, AR data will be summarized at each follow up visit.

Analysis Method:

AR will be presented with frequencies and percentages at screening, discharge and 1-year post procedure.

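### The exclusion of all echoes after a reintervention also reaches the discharge AR endpoint, so a subject re-treated for regurgitation before any discharge echo cannot be counted as a case

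*SAP*

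**What the plan says.** The FX secondary endpoints in SAP 9.3.2 include "Percentage of subjects with ≥ moderate aortic regurgitation (AR) at discharge". SAP 8.8.3 takes the result from the core-lab echocardiogram: "The parameter to be estimated is the grade of aortic valve regurgitation using echo, in subjects at discharge". For the FX Addendum, SAP 9.5 fixes the analysis set: "Echocardiography data will be analyzed based on the implanted set".

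SAP 9.5 repeats the rule of SAP 8.7: "Echocardiographic assessments after the first reintervention date will be excluded from any analyses using echo data". The sentence before it, on hemodynamic analyses, leaves room for exceptions to be specified; this one does not. The status itself comes from the Clinical Events Committee (CEC): "Reinterventions will be based on CEC adjudication".

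On missing data, SAP 8.3 says "Unless otherwise specified, no statistical techniques will be used to impute missing data" and adds "The number of subjects included in each analysis will be reported so that the reader can assess the potential impact of missing data". Protocol Table 2, footnote 6, sets the discharge TTE between 12 hours and 7 days after TAVR.

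**The concern.** Protocol 5.2 introduces the endpoints with "The following endpoints will be used to evaluate valve performance and procedural outcomes associated with the" FX system. A valve that leaked enough to be re-treated within days bears directly on that aim. Yet if the re-treatment comes before the discharge TTE, the only later echo is inadmissible and the subject drops out of the AR percentage for a reason tied to the outcome.

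The clearest case is a subject who still has moderate or worse AR after re-treatment. That subject meets the endpoint as written, but the echo that shows it is set aside. The study is descriptive, so the percentage is itself the result. The reported number analysed would show a smaller denominator without saying that the missing subjects had been re-treated for a leak.

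**Working it through.** The plan gives no AR rate, no reintervention rate and no calculation behind this endpoint, so there is no figure to reproduce. The check has two parts.

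**How the rules combine**

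1. The exclusion covers every analysis that uses echo data (SAP 8.7, 9.5). Discharge AR is such an analysis (SAP 8.8.3), and neither 8.8.3 nor 9.5 exempts it.
2. The TTE window runs from 12 hours to 7 days, so a reintervention can come first.
3. With no admissible echo there is no grade, so the subject cannot be a numerator case. This follows directly from the text.
4. With no imputation, and with the number analysed reported for each analysis, the natural reading is available-case, so the subject also leaves the denominator. This is an inference, because SAP 8.8.3 states no denominator rule.
5. A subject whose qualifying echo precedes the reintervention stays in, as does anyone whose AR is not re-treated. An echo on the same calendar day as the reintervention is not settled by the wording.

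**Size, on assumed inputs**

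- D = implanted subjects with either a gradable discharge echo or a re-treatment for regurgitation before it. Assumed 150 (the approximate sample size in SAP 9.4) or 141 (150 × 0.94). The 6% comes from SAP 8.3, where it concerns primary data at 12 months; it is borrowed here only to give a range.
- m = subjects with moderate or worse AR from the index valve, assumed 1 to 5.
- r = those of the m re-treated before any discharge TTE, assumed 0 to 2.

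Formulas:

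- SAP rule, available-case: (m − r)/(D − r)
- Re-treatment counted as failure, or AR still moderate or worse afterwards: m/D
- AR corrected and counted as absent: (m − r)/D

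| D | m | r | SAP rule | Failure or residual AR | Corrected AR |
|---|---|---|---|---|---|
| 150 | 1 | 1 | 0.00% | 0.67% | 0.00% |
| 150 | 3 | 1 | 1.34% | 2.00% | 1.33% |
| 150 | 4 | 2 | 1.35% | 2.67% | 1.33% |
| 150 | 5 | 2 | 2.03% | 3.33% | 2.00% |
| 141 | 1 | 1 | 0.00% | 0.71% | 0.00% |
| 141 | 3 | 1 | 1.43% | 2.13% | 1.42% |
| 141 | 4 | 2 | 1.44% | 2.84% | 1.42% |
| 141 | 5 | 2 | 2.16% | 3.55% | 2.13% |

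With r = 0 the three agree.

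Shortfall per affected subject = [m/D − (m − r)/(D − r)]/r = (D − m)/[D(D − r)]. For D = 150 it runs from 145/(150 × 149) = 0.649 points (m = 5, r = 1) to 149/(150 × 149) = 0.667 points (m = 1, r = 1). For D = 141 it runs from 136/(141 × 140) = 0.689 to 140/(141 × 140) = 0.709 points.

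If the AR was corrected, the SAP figure is higher by r(m − r)/[D(D − r)]. The largest values, at m = 5 and r = 2, are 6/(150 × 148) = 0.027 points and 6/(141 × 139) = 0.031 points.

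If the denominator were held at 150, the case would still be lost: 2/150 = 1.33% against 3/150 = 2.00%.

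A subject re-treated for another reason, without moderate or worse AR, shifts the figure slightly upwards: with three observed cases, 3/149 = 2.01% against 3/150 = 2.00%.

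Exact (Clopper-Pearson) 95% intervals overlap widely: 2/149, 0.16 to 4.76%; 3/150, 0.41 to 5.73%; 2/140, 0.17 to 5.07%; 3/141, 0.44 to 6.09%.

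**The case against.** The exclusion is coherent and pre-specified. An echo after a reintervention no longer describes the index result alone, and reinterventions rest on committee adjudication. This stands, and it is why the rule should stay.

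The affected group is narrow and may be empty. It needs an adjudicated reintervention, for regurgitation, before any qualifying echo. The supplied documents do not define reintervention, so it is unknown whether a corrective step within the index procedure counts. The parent protocol, to which Protocol 13.7 refers for missing data, was not available and may settle this. This stands as a limit on size, not on the reading of the text.

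Some disclosure is already planned. SAP 8.9 provides listings of adverse events, with dates, outcomes and procedure or device relatedness, and of device deficiencies. A reader could partly trace re-treated subjects from these, but nothing attaches the reason for exclusion to the AR result.

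Protocol section 6 bases echo endpoints on core-lab assessment, and a re-treatment decision is not a core-lab grade. This is correct, and it confines any failure-counting figure to a supplementary role.

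Finally, the size rests wholly on assumed counts, and the endpoint is descriptive. Both points are accepted, and they keep the priority low.

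**Conclusion.** The point holds at low priority. As written, the rule can remove a subject from discharge AR for an outcome-related reason, including one whose residual AR meets the written endpoint. In that case, or if re-treatment is read as index-valve failure, the percentage is too low by about 0.65 to 0.71 points per affected subject, given 141 to 150 evaluable subjects and the assumed counts. The number affected is unknown and may be zero.

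Two stronger readings are tempting but not supported. A reader might infer that the rule can only lower the percentage. That is true only for regurgitation re-treatments with residual AR or under the valve-failure reading; where AR was corrected, the figure rises by at most about 0.03 points, and removing subjects re-treated for other reasons can also raise it slightly. A reader might also take departure from the denominator as stated; only the loss from the numerator follows directly.

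**What to change.** Keep the exclusion, and keep the planned core-lab percentage on the implanted set as the main figure. In SAP 8.8.3 and 9.5, add:

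1. One pre-specified supplementary row for discharge AR, in which a CEC-adjudicated reintervention for regurgitation before the discharge TTE counts as moderate or worse AR and the subject stays in the denominator.
2. Beside it, the number of implanted subjects with no usable discharge grade because of an earlier reintervention, with the adjudicated reason and, where one exists, the core-lab grade after the reintervention.

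The cost is SAP wording, one derived flag, one table row and one count. Adjudication of reinterventions is already planned; the reason must also be captured if it is not already. The drawback is that the supplementary row classes some subjects who have no eligible core-lab grade, so it must stay supplementary. It may also look slightly less favourable than the main figure. If nobody is affected, the count reads zero and the reader knows that the percentage is complete in this respect.
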